2.2. Endpoints

Primary Endpoints

1. Overall comfort (Item: How would you rate the study contact lenses on: Overall Comfort; [REDACTED])
2. Comfort at the end of the day (Item: How would you rate the study contact lenses on: Comfort at the end of the day; [REDACTED])
3. Dryness at the end of the day (Item: How would you rate the study contact lenses on: Keeping your eyes from feeling dry at the end of the day; [REDACTED])

Each primary endpoint will be assessed at the 1-week follow-up evaluation using individual questionnaire items. All primary endpoints utilize an Excellence response set (0: Not Applicable, 1: Excellent, 2: Very Good, 3: Good, 4: Fair and 5: Poor).

Secondary Endpoints

1. Secondary Group 1: Comfort Performance
 - a. Comfort throughout the day (Item: How would you rate the study contact lenses on: Keeping your eyes feeling comfortable from morning to night; [REDACTED])

Response set : Excellence (0: Not Applicable, 1: Excellent, 2: Very Good, 3: Good, 4: Fair and 5: Poor).

2. Secondary Group 2: Digital Device Performance
 - a. Comfort while using digital devices (Item: How would you rate the study contact lenses on: Remaining comfortable while using computer screens and other digital devices (phones, tablets); [REDACTED])
 - b. Dryness while using digital devices (Item: How would you rate the study contact lenses on: Keeping your eyes from feeling dry while using computer screens and other digital devices (phones, tablets); [REDACTED])

Response set: Excellence (0: Not Applicable, 1: Excellent, 2: Very Good, 3: Good, 4: Fair and 5: Poor).

Clinical Study Protocol

Johnson & Johnson Vision Care, Inc.

3. Secondary Group 3: Performance at lens fitting

- a. Lens awareness upon insertion (Item: I lost awareness of these lenses shortly after inserting them (within one minute); [REDACTED])
- b. Comfort upon insertion (Item: These lenses were comfortable shortly after inserting them (within one minute); [REDACTED])

Response set: Agreement (1: Strongly disagree, 2: Disagree, 3: Neither agree nor disagree, 4: Agree and 5: Strongly agree)

4. Secondary Group 4: Lens Handling Performance

- a. Overall ease of handling (Item: How would you rate the study contact lenses on: Overall ease of handling the lenses (putting them on and taking them off); [REDACTED])
- b. Ease of insertion (Item: How would you rate the study contact lenses on: Ease of putting the lenses on your eyes; [REDACTED])

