4. STUDY DESIGN AND RATIONALE

4.1. Description of Study Design

This is a two-phase adaptive design. Each phase will be a multi-site 4-visit bilateral 2x2 dispensing crossover trial. In Phase I, approximately 65 subjects will be enrolled with a target of 60 subjects to complete. After Phase I, an interim analysis will be conducted to determine the number of subjects that will be enrolled into phase II if the study continues; a maximum of up to 300 additional subjects maybe enrolled.

The subjects enrolled in each phase will be randomized separately. Whenever possible, the same clinical sites will be used to enroll subjects throughout the entire course of the study. Furthermore, both phases will utilize the same crossover design and will be conducted as follows: at Visit 1 (Day 0), eligible subjects will be randomized to one of two lens wear sequences (O1D/P1 or P1/O1D). Subjects will be dispensed their first study lens per the randomization scheme and will wear the study lenses for 6 to 8 days and return for their follow-up evaluation (Visit 2). Study measurements will be performed, and subjects will be instructed to wear their habitual contact lenses or spectacles for a period of 6 to 8 days. Subjects will then return for Visit 3 not having worn their habitual contact lenses the day of the visit and will be dispensed their second study lens. Subjects will return for their follow-up evaluation and final

Clinical Study Protocol

Johnson & Johnson Vision Care, Inc.

visit (visit 4) 6 to 8 days after Visit 3. Study measurements will be performed, and the subject will exit from the study.

Study lenses are to be worn as daily disposable. Unscheduled visits may occur during the course of the study. Any unworn lenses are to be collected prior to the subject being exited from the study.

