5. TEST ARTICLE ALLOCATION AND MASKING

5.1. Test Article Allocation

The randomization scheme will be provided by the study responsible biostatistician for each phase separately. In both phases, the study randomization will be stratified by site. Eligible subjects will randomly be assigned to one of two unique lens wear sequences (O1D/P1 or P1/O1D) using permuted block randomization in block sizes of 2, to avoid bias in the assignment of subjects to treatment, and to enhance the validity of statistical comparisons between treatment groups. The randomization scheme will be generated using the Statistical Analysis System (SAS) software Version 9.4 or higher⁷ (SAS Institute, Cary, NC).

Clinical Study Protocol

Johnson & Johnson Vision Care, Inc.

The study site will follow the randomization scheme provided and will complete enrollment according to the randomization list and will not pre-select or assign subjects. Randomization will be performed at Visit 1 of each phase. The following must have occurred prior to randomization:

- Informed consent must have been obtained.
- The subject must have met all eligibility criteria.
- The subject's screening and baseline information must have been collected.

When dispensing test articles, the following steps should be followed to maintain randomization codes:

1. Investigator or designee (documented on the Delegation Log) will consult the lens fitting schedule to obtain the test article assignment for that subject prior to dispensing.
2. Investigator or designee will record the subject's number on the appropriate line of the lens fitting schedule
3. Investigator or designee will pull the appropriate test articles from the study supply. All test articles that are opened, whether dispensed (placed/fit on eye or dispensed outside the clinical site) or not, must be recorded on the Test Article Accountability Log in the "Dispensed" section.

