$$\begin{aligned}H_0: OR &\leq 0.67 \\H_a: OR &> 0.67\end{aligned}$$

Where, the OR represents the odds of having a more positive experience (Excellent or Very Good) while wearing O1D compared to P1. Non-inferiority of O1D relative to P1 will be concluded if the lower limit of the 97.5% CI is above 0.67 (using 10% as non-inferiority margin and assuming a reference proportion of 0.5).

Clinical Study Protocol

Johnson & Johnson Vision Care, Inc.

Sample size Estimation for Phase II

If non-inferiority is demonstrated for the primary endpoints, the sample size required to test superiority for each primary endpoint will be estimated. The odds ratio and the cumulative log-odds from the model described above for each endpoint will be used to create a new dataset with the same structure and design as Phase I. This new dataset will then be analyzed using the same model. The statistical power of each endpoint will be calculated using the F-statistics as $\text{Power} = P(F[F_{\text{crit}}, v, ncp] > F_{\text{crit}})$; where F_{crit} is the critical value of the central F distribution ($F_{\text{crit}} = F_{\text{numdf}, \text{dmdf}, 0, \alpha}$) under H_0 (H_0 : centrality param = 0), v is the magnitude of the departure from H_0 and ncp is the non-centrality parameter (Stroup).⁹

Phase II

Overall comfort, Comfort at the end of the day, and Dryness at the end of the day

Subjective responses to each primary endpoint will be grouped as: $aval=1$ is a subject responds' 'Excellent' or 'Very Good', $aval=2$ is a subject responds' 'Good' and $aval=3$ if a subject responds' 'Fair' or 'Poor'. $Aval$ will be analyzed separately for each primary endpoint using a generalized linear mixed model with a multinomial distribution and the cumulative logit as the link function. In each model, sequence of lens wear, period and lens type will be included as fixed effects. Site and subject nested within site will be included as a random effect. Errors between measurements within the same subject across study periods will be modeled using an unstructured covariance (UN) structure. Comparisons between O1D and P1 will be carried out using 1-sided 97.5% confidence intervals (CIs) constructed for the odds ratio (O1D over P1). Superiority of O1D relative to P1 will be concluded if the lower limit of the 97.5% CI is above 1.

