14.6. Secondary Analysis

All secondary items will be analyzed individually regardless of grouping and will model using the same model as described for the primary endpoints in Phase II above. Comparisons between O1D and P1 will be carried out using 1-sided 97.5% confidence intervals (CIs) constructed for the odds ratio (O1D over P1). For Secondary Group 1 – Comfort Performance and Secondary Group 2- Digital Device Performance, superiority of O1D relative to P1 will be concluded if the lower limit of the 97.5% CI is above 1. For Secondary Group 3 – Performance at Lens Fitting and Secondary Group 4- Lens Handling Performance, non-inferiority of O1D relative to P1 will be concluded if the lower limit of the 97.5% CI is above 0.67 (using 10% as non-inferiority margin and assuming a reference proportion of 0.5).

Note. $Aval$ will be derived as follows for Secondary Group 3 – Performance at Lens Fitting; $aval=1$ if a subject responds' 'Strongly Agree' or 'Agree', $aval=2$ if a subject responds' 'Neither Agree Nor Disagree' and $aval=3$ if a subject responds' 'Strongly Disagree' or 'Disagree')

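### The Phase II model asks for both a subject random intercept and an unstructured error covariance from two ordinal ratings per subject; these cannot be separated, so the model cannot be fitted as written

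*Combined protocol and SAP*

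**What the plan says.** Section 14.5 (Phase II) analyses a three-category rating "using a generalized linear mixed model with a multinomial distribution and the cumulative logit as the link function". Sequence, period and lens type are fixed effects. Two further sentences describe the dependence within a subject. One sets the random part of the model: "Site and subject nested within site will be included as a random effect". The other turns to the two ratings that a subject gives and adds a second covariance for them: "Errors between measurements within the same subject across study periods will be modeled using an unstructured covariance (UN) structure".

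Section 14.6 applies this model to every secondary item. Section 14.7 repeats both sentences for the exploratory digital-device analysis.

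The design is a 2x2 crossover (Section 4.1). On the timing of the primary ratings, Section 2.2 says: "Each primary endpoint will be assessed at the 1-week follow-up evaluation using individual questionnaire items". Secondary Group 3 is rated at each lens fitting instead. Either way, a subject contributes two ratings per item.

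The decision rules differ. The Phase II primary endpoints and Secondary Groups 1 and 2 are tested for superiority against an odds ratio of 1. For Secondary Groups 3 and 4, "non-inferiority of O1D relative to P1 will be concluded if the lower limit of the 97.5% CI is above 0.67"; Section 14.7 uses the same limit. The limit is explained as "using 10% as non-inferiority margin and assuming a reference proportion of 0.5". Phase I also uses 0.67, but in a model with fixed effects only and no subject term.

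**The concern.** A random subject intercept already describes how a subject's two ratings go together. A 2x2 unstructured matrix describes the same thing again with three more parameters. With only two ordinal ratings per subject, and no residual variance to estimate on the logit scale, the data cannot tell the two apart. The specification therefore has no unique solution, and nothing in the text says which component gives way.

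A second question arises once the intercept is kept. The lens odds ratio is then conditional on the subject. The margin of 0.67 was obtained from proportions, which are population quantities. Away from 1 the two kinds of odds ratio differ, so a limit derived on one scale does not mean the same thing on the other.

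At stake are a model that can be run as pre-specified for every Phase II test, and the meaning of the margin for the five items in Secondary Groups 3 and 4 and for the exploratory comparisons.

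**Working it through.** **Inputs from the documents.** Three ordered categories, cumulative logit, random effects for site and subject within site, unstructured error covariance (Section 14.5); two periods with one rating each (Sections 2.2 and 4.1); 10-point margin at reference 0.5 (Sections 14.5 to 14.7). The between-subject variance is not given and is assumed over a range.

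**1. The plan's own margin.** (0.40/0.60) / (0.50/0.50) = 0.667, which rounds to 0.67. A relative 10% reading (0.45 against 0.50) gives 0.818 and does not match. So 0.67 represents 10 absolute points in overall proportions.

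**2. Identifiability.** Write the subject's linear predictor in period j as fixed effects + b + e_j, with Var(b) = s² and (e_1, e_2) having variances v1, v2 and covariance c. The likelihood sees only the sums

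- period 1 variance: v1 + s²
- period 2 variance: v2 + s²
- covariance: c + s²

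That is four parameters for three sums. Lowering s² by d and raising v1, v2 and c by d changes nothing. Numerical check with assumed values s² = 1.0, v1 = 1.0, v2 = 1.3, c = 0.5: moving 0.6 gives 0.4, 1.6, 1.9, 1.1, and the sums stay 2.0, 2.3 and 1.5. The largest change in any cell probability was 0.0. The information matrix was singular (smallest scaled eigenvalue about 1e-16), with exactly this trade as its null direction. More subjects do not cure it.

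If the unstructured matrix is instead a residual covariance, a multinomial outcome has no free residual variance, and the single within-subject association is already carried by b.

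**3. Each component alone, at 300 subjects (assumed parameter values).**

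| Component kept | Smallest scaled eigenvalue | SE of lens log odds ratio |
|---|---|---|
| Intercept only | 0.21 | 0.18 |
| Unstructured, as period-specific random effects | 0.0006 | 0.75 |

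In the second row the two variances themselves have standard errors of about 17 and 18.

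**4. What 0.67 means with the intercept kept.** Latent intraclass correlation ICC corresponds to s² = ICC/(1 − ICC) × π²/3. With the reference lens at 50% overall, the overall proportion on the test lens is the average of expit(log 0.67 + b) over b ~ N(0, s²).

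| Assumed ICC | s² | Overall proportion at subject-specific 0.67 | Loss (points) | Subject-specific OR matching a 10-point loss |
|---|---|---|---|---|
| 0 | 0 | 0.401 | 9.9 (10.0 with unrounded 0.667) | 0.67 |
| 0.2 | 0.82 | 0.416 | 8.4 | 0.62 |
| 0.5 | 3.29 | 0.436 | 6.4 | 0.53 |
| 0.7 | 7.68 | 0.451 | 4.9 | 0.44 |

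A subject-specific odds ratio of 1 gives a population odds ratio of 1 at every variance.

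**5. Simulation.** Crossovers of 1,000 subjects (12 replicates, subject SD 2 logits), fitted with and without the intercept: true subject-specific 0.67 gave 0.65 and 0.77; true 1.0 gave 1.02 and 1.01.

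**The case against.** The strongest reply is that little depends on this. The Phase II primary tests and Secondary Groups 1 and 2 are against 1, where both scales share the null. The Phase I test has no subject term. Section 14.4 lets Groups 3 and 4 be tested only after all primary hypotheses and Groups 1 and 2 have succeeded, and the exploratory tests only after the primary hypotheses and Group 2. The margin discrepancy is conservative. All of this stands, and it limits the margin point. It does not rescue a model that has no unique fit.

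The 10-point equivalence is also only nominal. With no subject effect at all, 0.67 is a loss of 9.0, 7.2 and 4.2 points at assumed references of 0.7, 0.8 and 0.9. That stands too: a population-averaged odds ratio recovers 10 points only near the stated reference.

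Section 14.1 defers detail to a stand-alone SAP to be finalised before database lock, and Sections 5.2 and 5.3 keep the mask until then. A reader might infer that the choice of component is open to being made on the results. The documents do not show that. They show only that the text available here does not make the choice; the stand-alone SAP may.

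A reader might also infer that dropping one term rather than the other necessarily changes the odds ratio. That follows only if the errors are a residual covariance. If they are period-specific random effects, the odds ratio stays subject-specific and the problem is poor precision, as step 3 shows.

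**Conclusion.** The specification in Sections 14.5 and 14.7, inherited by Section 14.6, cannot be fitted as written. This is a structural result; it depends on no assumed variance and holds on either reading of the errors. Keeping the intercept alone leaves a well-determined model.

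The margin point is separate and smaller. It comes from the random intercept itself and would exist without the unstructured sentence. Its size rests on an ICC that the documents do not give: the permitted loss is 8.4 to 4.9 points over ICC 0.2 to 0.7, instead of 10, at reference 0.5. It costs power on the five items of Secondary Groups 3 and 4 and on the exploratory comparisons; the power loss itself was not calculated.

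The stronger inference, that the mismatch could yield a false non-inferiority claim or undermine the primary result, is not supported. At reference 0.5 the subject-specific limit is stricter than the stated margin, and the null of 1 is the same on both scales.

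**What to change.** 1. Delete the unstructured-covariance sentence in Sections 14.5 and 14.7 and keep the random effects for site and subject within site. Section 14.6 then needs no separate edit. Cost: wording only.
2. For Secondary Groups 3 and 4 and the exploratory analysis, compute the population-averaged odds ratio by marginalising the fitted model over the random effects, and compare the lower limit of its confidence interval with 0.67. Name the cut point at which it is evaluated, since the marginalised value can differ between cut points; the most favourable category agrees with how Section 14.5 defines the odds ratio for Phase I. Cost: one extra estimation step, including an interval for the marginalised quantity.
3. Record both choices, and state which odds ratio is reported for the superiority tests, before unmasking.

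Visits, randomisation and data collection do not change.

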14.6. Secondary Analysis

All secondary items will be analyzed individually regardless of grouping and will model using the same model as described for the primary endpoints in Phase II above. Comparisons between O1D and P1 will be carried out using 1-sided 97.5% confidence intervals (CIs) constructed for the odds ratio (O1D over P1). For Secondary Group 1 – Comfort Performance and Secondary Group 2- Digital Device Performance, superiority of O1D relative to P1 will be concluded if the lower limit of the 97.5% CI is above 1. For Secondary Group 3 – Performance at Lens Fitting and Secondary Group 4- Lens Handling Performance, non-inferiority of O1D relative to P1 will be concluded if the lower limit of the 97.5% CI is above 0.67 (using 10% as non-inferiority margin and assuming a reference proportion of 0.5).

Note. $Aval$ will be derived as follows for Secondary Group 3 – Performance at Lens Fitting; $aval=1$ if a subject responds' 'Strongly Agree' or 'Agree', $aval=2$ if a subject responds' 'Neither Agree Nor Disagree' and $aval=3$ if a subject responds' 'Strongly Disagree' or 'Disagree')

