14.4. Level of Statistical Significance

All type I error adjustments utilized in this study were calculated using a Bonferroni¹⁰ correction.

Primary hypotheses in Phase I will be tested using a familywise type I error rate of 5%; each hypothesis will be tested using an individual type I error rate of 1.67%.

Hypotheses in Phase II will be tested using the following strategy:

Primary hypotheses will be tested using a familywise type I error rate of 5%; each hypothesis will be tested using an individual type I error rate of 1.67%. All primary hypotheses must be met in order to test any secondary hypotheses. Secondary hypotheses were grouped according to item semantic similarities. Each secondary hypothesis group will be tested using an overall type I error rate of 5% and in a sequential order. Each preceding secondary hypothesis group must be fully met in order to continue testing the remaining secondary hypotheses. Exploratory hypotheses will only be tested if all primary and secondary group 2 hypotheses are met.

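### Section 14.6 decides each of the three Group 4 handling items at 1-sided 2.5%, where Section 14.4's Bonferroni rule at 5% per group gives 1.67%

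*Combined protocol and SAP*

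**What the plan says.** Protocol Section 14.4 sets the error rates. Its general rule is "All type I error adjustments utilized in this study were calculated using a Bonferroni" correction. For the three primary hypotheses it fixes a 5% family rate and states that "each hypothesis will be tested using an individual type I error rate of 1.67" per cent. For the secondary hypotheses it says "Each secondary hypothesis group will be tested using an overall type I error rate of 5% and in a sequential order". It does not say whether that 5% is 1-sided or 2-sided, and it writes out no per-item level for any secondary group. Two gates apply: "All primary hypotheses must be met in order to test any secondary hypotheses", and "Each preceding secondary hypothesis group must be fully met in order to continue testing the remaining secondary hypotheses".

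Section 2.3 lists one hypothesis in Group 1, two in Group 2, two in Group 3 and three in Group 4 (overall handling, insertion, removal).

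Section 14.6 gives the decision rule. Its opening words, "All secondary items will be analyzed individually regardless of grouping", introduce the model shared by all items. The level follows in the next sentence: "Comparisons between O1D and P1 will be carried out using 1-sided 97.5% confidence intervals (CIs) constructed for the odds ratio (O1D over P1"). For Groups 3 and 4, "non-inferiority of O1D relative to P1 will be concluded if the lower limit of the 97.5% CI is above 0.67".

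**The concern.** Group 4 is a family of three hypotheses with an overall 5%. Section 14.4 meets the same case among the primary endpoints and assigns 1.67% to each. Section 14.6 assigns 2.5% to each handling item instead, so the stated decision rule does not deliver the stated group error rate.

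The three handling claims are at stake. On the 1-sided reading, a handling item with a 1-sided p-value between 0.0167 and 0.025 succeeds under Section 14.6 and fails under Section 14.4. Nothing in the plan says which section governs, so the choice could be made after the results are known.

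**Working it through.** **Inputs.** Group error 5%, Bonferroni, and the worked level of 1.67% (Section 14.4). Group sizes 1, 2, 2, 3 (Section 2.3). Per-item level 1 − 0.975 = 0.025, 1-sided (Section 14.6). The documents give no correlation between items, so a range is assumed.

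**Step 1: reproduce the plan's own figure.** Bonferroni for three hypotheses at 5%: 0.05 / 3 = 0.01667, which is the 1.67% in Section 14.4.

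**Step 2: error spent by Section 14.6 in each group, taking the 5% as 1-sided.** Bonferroni sum = k × 0.025.

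| Group | k | Level implied by 14.4 (5%/k) | Matching 1-sided bound | Sum at 2.5% per item | Within 5%? |
|---|---|---|---|---|---|
| 1 | 1 | 5% | 95% | 2.5% | yes |
| 2 | 2 | 2.5% | 97.5% | 5.0% | yes |
| 3 | 2 | 2.5% | 97.5% | 5.0% | yes |
| 4 | 3 | 1.67% | 98.33% | 7.5% | no |

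**Step 3: chance of at least one false Group 4 claim.** Take all three items exactly at the margin (odds ratio 0.67). With independent items this is 1 − 0.975³ = 0.0731. With equal correlation ρ between normal test statistics and critical value c = 1.960, it is 1 − ∫ φ(x) Φ((c − √ρ·x)/√(1 − ρ))³ dx. For 1.67% per item, c = 2.128.

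| Assumed ρ | 2.5% per item (14.6) | 1.67% per item (14.4) |
|---|---|---|
| 0 | 7.31% | 4.92% |
| 0.3 | 6.83% | 4.65% |
| 0.5 | 6.27% | 4.29% |
| 0.7 | 5.46% | 3.75% |
| 0.8 | 4.91% | 3.37% |

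The 2.5% column equals 5% at ρ = 0.785.

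**Step 4: the 2-sided reading.** A 2-sided 5% leaves 2.5% in the claimed direction. The sums of 5.0% (Groups 2 and 3) and 7.5% (Group 4) then exceed it, and Group 1 meets it exactly. The matching 1-sided bounds are 97.5% (Group 1), 1 − 0.025/2 = 98.75% (Groups 2 and 3) and 1 − 0.025/3 = 99.17% (Group 4).

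**The case against.** The best defence is that Group 4 can be claimed only as a whole. Section 2.3 words the hypothesis as non-inferiority on each of the three items, and Section 14.4 speaks of groups being fully met. If all three must pass, a false group claim has probability at most 2.5% and no adjustment is needed. That rule would be sound, but the plan does not state it. The fully-met condition applies to preceding groups, as a gate, and no secondary group follows Group 4. The plan also applies Bonferroni to the primary hypotheses, all three of which must be met before secondary testing starts, so by its own convention a joint requirement does not replace the adjustment.

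A second defence concerns size, and much of it stands. Independence is unlikely: items were grouped by similar meaning, and the overall handling item is described as putting the lenses on and taking them off, which is what the other two items rate. At a correlation of 0.7 the excess is about half a percentage point, and from about 0.79 upward there is none. Group 4 is also reached only after eight earlier hypotheses succeed (three primary, then 1 + 2 + 2), six of them superiority. The figures above describe the Group 4 step alone. However, Section 14.4 promises 5% for each group, and Bonferroni does not rely on a correlation to keep that promise.

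A third defence is that the stand-alone SAP foreseen in Section 14.1 will settle the level. Section 14.6 already states an explicit rule, and Section 14.10 commits the analysis to both documents, so a different level there would conflict with the protocol unless the protocol changes too.

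**Conclusion.** The point holds for Group 4. Its Bonferroni sum is 7.5% against a stated 5%. The group-wise error is 7.3%, 6.3% or 5.5% at assumed correlations of 0, 0.5 or 0.7, and at or below 5% only from about 0.79 upward. These figures assume that Group 4 is reached, that all three items lie at the margin, and that single-item claims are open.

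A reader might infer more, and the documents do not support it:

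- *That Section 14.6 deliberately sets error rates without regard to group size.* The words about grouping describe how items are modelled; the conflict comes from the confidence level in the sentence after them.
- *That no single level could serve all four groups.* A common 1-sided 1.67% would keep every group within 5%. Section 14.4 does not require each group to spend exactly 5%.
- *That Group 1 is wrongly tested.* At 1-sided 2.5% it is conservative. A 95% bound would be a preference for power, and the plan states no power for any secondary endpoint.
- *That Groups 2 and 3 are also too lenient.* This is so only if the 5% is 2-sided. The confidence-interval comparisons in Sections 14.5 to 14.7 are all 1-sided, so the 1-sided reading is better supported, although Section 14.4 should say so.

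This affects the last secondary group only, but it is a clear inconsistency in a pre-specified rule and is cheap to remove.

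**What to change.** In Section 14.4, state that the 5% per secondary group is 1-sided. Then choose one of two rules for Group 4:

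1. In Section 14.6, conclude non-inferiority for a handling item only if the lower limit of its 1-sided 98.33% confidence interval is above 0.67.
2. In Sections 14.4 and 14.6, state that Group 4 is claimed only if all three items pass at the 97.5% bound, and exempt that group from the general Bonferroni sentence.

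Groups 1 to 3 keep the 97.5% bound. If the sponsor intends a 2-sided 5%, 98.33% is not enough: the bounds become 98.75% for Groups 2 and 3 and 99.17% for Group 4, with Group 1 unchanged at 97.5%.

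The cost is wording, with no extra subjects or data. Under option 1 the distance from estimate to lower limit on the log-odds scale grows by 2.128 / 1.960 = 1.086, about 9%. An item with an assumed 80% power at 2.5% (shift 1.960 + 0.842 = 2.802) would have Φ(2.802 − 2.128) = 0.750, about 75%, at 1.67%. Option 2 keeps the present bound but gives up claims on single handling items.

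The primary endpoints show a parallel mismatch between 1.67% in Section 14.4 and the 97.5% bounds in Section 14.5. Correcting Section 14.5 alone would leave Section 14.6 as it is, so both sections should be tied to the levels in Section 14.4 in the same revision.
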